5. WORK PACKAGE 3 -DESCRIPTIVE STUDY OF PATIENT CHARACTERISTICS, RESPECT PLAN

CHOICE AND RISK OF HARM

5.1 Study Design

Retrospective observational study

Sampling: Six acute hospitals selected for work package one

Inclusion criteria: Adult in-patients

Exclusion criteria: Paediatrics, Neonates, day case admissions, refusal of consent.

5.1.1 Aim

The overall aim of this work package is to explore how widely ReSPECT is being used amongst

patients in hospital and to examine associations between recommendations and patient

ReSPECT Evaluation Protocol Version 5.0, dated 20.06.19, IRAS project ID: 204688 characteristics and their outcomes.

Within this broad framework, we will explore if DNACPR recommendations which are made in the context of an overall ReSPECT increase the risk of certain harms when compared with not having a DNACPR order in place.

This work package will also provide a broad understanding about how the ReSPECT process is used in practice.

5.1.2 Objectives

To present a descriptive summary of ReSPECT use in hospitalised patients, explore their relationship with patient characteristics and conduct an analysis of whether a DNACPR decision, made in the context of an overall treatment plan is independently associated with risk of patient harm.

5.1.3 Research Questions

- 1. What combinations of emergency care and treatment plans are recorded on ReSPECT. How are they related to patient characteristics and overall outcomes of patients?
- 2. Which patient characteristics predict assignment to particularly emergency care and treatment plans?
- 3. Which patient characteristics predict assignment to a DNACPR?
- 4. Do particular patient preferences and emergency care and treatment recommendations predict a DNACPR decision?
- 5. Is a DNACPR decision an independent predictor of patient harm?

5.1.4 Methods

We will conduct a retrospective case-note review that is synchronised with the routine collection of NHS Safety Thermometer data. In addition information on patient demographics, admission, comorbidities and functional status and ReSPECT decisions (or absence of ReSPECT decisions) will be extracted from clinical records. We will explore the associations between patient characteristics, resuscitation status, care group and risk of harm.

Assessments will be co-ordinated to occur simultaneously with the routinely collected NHS Thermometer Audit data. The majority of NHS Trusts contribute to the NHS Safety Thermometer programme. In the event that a research site does not routinely collect NHS Safety Thermometer data (or the national programme is unexpectedly withdrawn) they will be asked to collect Classic Safety Thermometer data for research purposes.

5.2 Recruitment and withdrawals for WP3

The intention is to assess in-patients across all clinical areas at participating hospital sites. Each in-patient clinical area will be assessed only on one occasion. As described in section 2.3 Ethical Considerations, information collected about a patient will be withdrawn in the event that a patient (or their legal representative or family member) advises the patient would not have wanted to take part in this way when they did have capacity to make their own decisions.

Patients will not only be able to inform the team they do not wish their information to be included in the study prior to data collection, but that they can also contact the team until the data set is locked for analysis to request their data are not used. The local contact will either remove the data from the data set, if data collection is still in progress. If the data set has been returned to the central study team, the local researcher will inform the study team giving the participants study ID and site ID. The study team will remove the data from the data set and record the action in the Study Master File in the appropriate section.

5.3 Data Collection for WP3

The following information will be extracted from the clinical and audit/or records:

(1) Demographics (age, gender, ethnicity, abbreviate home postcode as a proxy for social class), (2) Reason for admission, (3) Co-morbidities: Cognitive impairment (dementia, learning difficulties), Charlson co-morbidity index [56], GO-FAR sore [57] (both of which predict outcome from cardiac arrest), assessment of whether their condition is likely to be fatal (measured by McCabe Scale [58]), (4) ReSPECT (patient preference, emergency care treatment decisions, resuscitation status, capacity, who was involved in the discussions, when, where and by whom was the decision made), (5) NHS Safety Thermometer Audit data, (6) Length of hospital stay, survival to discharge, discharge location.

We will endeavour to ensure that researchers collect baseline data blind to ReSPECT classification. Practically what this means is that the researcher will first extract the baseline data, some of which may need some interpretation. Only when this is complete will they extract ReSPECT classification data which does not require any interpretation.

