We are seeking approval from the Confidentiality Advisory Group to use section 251 of the NHS Act 2006 to access medical records. Patients will be given the opportunity to opt out of this part of the study by the provision of information leaflets and posters explaining the study. We present the potential risks, mitigations and benefits of this approach below.

The main risk for copying and extracting data from clinical records relates to a breach of trust / confidentiality through access to clinical records. We are mitigating the risk by (1) only reviewing sections of the record relevant to the research question (2) collecting the minimum amount of data to address this research question (3) anonymising copied/extracted data (4)

making use of routine audit data where possible (5) ensuring staff collecting the data will have a duty of confidentiality through a contract with the hosting NHS Trust. It is possible (although unlikely, given the existing duty of clinicians to consult patients), that an awareness of this research activity may prompt patients to raise questions about their overall treatment.

The direct benefits for individual research participants are limited to raising a general awareness about ReSPECT amongst clinical staff and patients. There will also be benefits for future patients through a better understanding of how ReSPECT is working in the NHS.

Considering the risks, mitigations and benefits we assess the overall risks from this as low to negligible.

The research requires the research team to access the following information from the patients' clinical records

- i) Information recorded on the ReSPECT form
- ii) Clinical justification for a ReSPECT recommendation
- iii) General information about the patient (Full information is provided in protocol section 5.3). The types of information required is e.g. demographic information, severity of illness measures and laboratory results.

This information will be linked by hospital based research staff to hospital held information on:

- iv) NHS Safety Thermometer data for each individual patient
- v) Overall outcome for each individual patient (length of hospital stay, survival to discharge, discharge location type)

Information will be copied or extracted from the ReSPECT form and clinical records by NHS research staff. This will be linked with information from the NHS Thermometer measurements and outcome information (length of stay, survival, discharge location type).

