5.3.1 Outcomes

As our measure of patient harm we will use the data collected for the NHS Safety Thermometer. In participating Acute Trusts this point of care survey collects data on 100% of inpatients for one day each month. Our outcome of interest in the Classic Thermometer is 'harm free care' defined as none of the defined adverse events being present on the day of the assessment (pressure ulcers, urine infections in catheterised patients, falls, or venous thromboembolism). These are all events that would be associated with less intense care. If as a consequence of a DNACPR order, there are more of these events we will conclude that more work is needed to prevent iatrogenic harms caused by DNACPR orders leading to a lower level of care.

A second harm measure, the 'Medication Thermometer', is being rolled out in the NHS. This also a point of care survey collecting data on 100% of in-patients for one day each month. Our outcome of interest here is 'drug induced harm'. The survey identifies people who are using a specified list of high-risk medicines. There is then a discussion between a nurse, doctor and a pharmacist to assess if the patient has been harmed and the level of any harm. Harm will be defined as a moderate (or greater) incident which results in a moderate increase in treatment and which caused significant but not permanent harm. We will collect Medication Thermometer data where it is routinely available.

Standardisation of Data collection: NHS Safety Thermometer data will be extracted by NHS audit, clinical or site research staff who have been trained in the use of the tool. We are aware of variation in Thermometer measurements and will develop a training set of standardised cases in to improve consistency. We will work closely with the six sites to ensure the approach is standardised and report on reliability from the standardised cases.

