5.5 Data Analysis for WP3

Descriptive statistics will be used to summarise patient characteristics and outcomes according to patient personal preference, ReSPECT clinical treatment recommendation and resuscitation status. We will use appropriate multiple regression techniques to explore the associations between patient characteristics, resuscitation status (DNACPR or for resuscitation), care group and risk of harm and death. Firstly, by fitting a series of nested models with DNACPR (yes/no) as the dependent variable and patient characteristics and clinical treatment recommendation as indicated on the ReSPECT form) as the independent variables we will assess the influence of patient characteristics at baseline and patient preference on DNACPR decision and establish whether the patient preference adds information beyond that provided by the patient characteristics as regards the DNACPR decision. Secondly, we will use ordered logistic regression with care group ('Focus on Life-Sustaining Treatment' and 'Focus on Symptom Control' and 'No Decision') as the dependent variable and patient characteristics as the independent variables to assess whether patient characteristics influence the choice of care group. Finally, we will use logistic regression (conditional should we be able to match cases to controls), with and without adjustment for patient characteristics, with harm (yes/no, obtained from the NHS Safety Thermometer) as the dependent variable and care group ('Focus on LifeSustaining Treatment' and 'Focus on Symptom Control') and DNACPR (yes/no) as independent variables to assess whether focus of care group or DNACPR order independently influence risk of harm.

Sample size: As this is an exploratory analysis a formal sample size calculation is not appropriate.

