Nevertheless, for generalisability we need to ensure a reasonable spread of patients/decisions, and in order to model risk of harm we need sufficient harmful events to have occurred. Based on our pilot data we expect 70% of patients to have a ReSPECT decision, of whom 20% will have a DNACPR decision. 20-30% will have no decision, which by default means they would receive resuscitation in the event of cardiac arrest. We therefore intend to enrol 3000 patients in this study (minimum 500 patients per site, six sites). Assuming a "harm rate" of 6.5% (based on 2014 NHS Thermometer data), this will provide 200 incidences of harm for the risk modelling. If possible, for the modelling of harms, we will match cases to controls in order to increase statistical power.

6. WORK PACKAGE 4 - FOCUS GROUPS WITH GENERAL PRACTITIONERS, COLLECTION OF CONTEXTUAL DATA ON IMPLEMENTATION AT SITES, SYNTHESIS OF FINDINGS AND IDENTIFICATION OF AREAS FOR IMPROVEMENT AND FURTHER WORK

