ordinating centre researchers and/or the study co-ordinator or study administrator to monitor the quality of CRFs. Data entered into the study database will be checked for accuracy in accordance with the WCTU SOPs and study Data Management Plan. The study electronic database will have quality control measures where possible, e.g. will not allow entry of data outside pre-set limits. Quality assurance checks on eligibility, completion of data, and the consent process will ideally be carried out during the data collection period at the site. Any issues identified will be recorded and then raised and discussed with the site research team and action agreed to ensure improved quality of data collection. As data is collected at only one time point at each site and this collection is likely to be completed within a fairly short time period, a pragmatic approach will need to be taken.

The quality of the NHS thermometer data — the study co-ordinating centre researchers and study co-ordinator will develop an approach and then work with trusts to ensure a consistent approach to data collection across sites. Each site is likely to have its own quality checks/processes to ensure it returns the best data to the national audit. The co-ordinating centre study team will work with the local audit departments and use existing local quality assurance processes. Again any process will be pragmatic due to data being collected on inpatients on a particular day at each site and the fact that we are using routinely collected audit data. Once the anonymised data set is returned to WCTU a random sample will be checked to ensure they are anonymised, to check the proportion linked between the CRF data and the NHS thermometer data and to check any variables that are consistently missing across cases, so any problems with the data quality or linkage can be resolved prior to analysis.

Visits to Sites: As data collection for WP1 is mostly going to be conducted by the co-ordinating centre researcher(s) initiation visits will be staggered to co-inside with the data collection. Each site will need a training visit prior to commencement of data collection for WP3. This training will be recorded on a log to keep who has received training and stored in the trial master file. If data has not yet been collected for WP1 at a site, the training and initiation visit is likely to be combined.

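### WP3 would tabulate whole-admission length of stay by ReSPECT and DNACPR status in a one-day census, so any decisions made after admission create a stay gap with no true difference

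*Protocol*

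**What the plan says.** WP3 is a census. Protocol section 5.2 says "Each in-patient clinical area will be assessed only on one occasion". Section 5.3.1 says of the Safety Thermometer, with which data collection is synchronised, that "this point of care survey collects data on 100% of inpatients for one day each month". Section 8 refers to "data being collected on inpatients on a particular day at each site".

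Stay is an outcome. Section 5.3 lists "6) Length of hospital stay, survival to discharge, discharge location" among the extracted items, and section 2.3 describes the same items as "Overall outcome for each individual patient (length of hospital stay, survival to discharge, discharge location type".

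Outcomes are set against decisions. Research question 1 in section 5.1.3 asks of the recorded plans "How are they related to patient characteristics and overall outcomes of patients". Section 5.5 answers: "Descriptive statistics will be used to summarise patient characteristics and outcomes according to patient personal preference, ReSPECT clinical treatment recommendation and resuscitation status".

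On timing, section 2.1 gives a planning figure of about 70% of in-patients with the process completed at admission, about 20% of these with DNACPR. It also names acute deterioration, a new life-limiting diagnosis and functional decline as prompts. Section 3.2.4 (WP1a) has the researcher check again after 48 hours for forms completed later. Section 5.3 collects when the decision was made. Nothing in section 5 starts the stay at the assessment day or at the decision.

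**The concern.** Whole-admission stay includes time before the assessment day and, for some patients, time before the decision. A patient three weeks into a stay has had more opportunity to acquire a ReSPECT form or a DNACPR decision than one admitted yesterday. Grouping by status therefore partly groups by time already spent in hospital, and that time is then reported as outcome. Research question 1 could show longer stays in the decision group even if decisions had no bearing on discharge.

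A second, separate effect is that a one-day census catches a stay with probability proportional to its length. Short stays, including early deaths, are under-represented. This shifts the absolute stay and survival figures. It does not by itself separate the groups.

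**Working it through.** **Inputs from the protocol.** Section 5.5: "we expect 70% of patients to have a ReSPECT decision, of whom 20% will have a DNACPR decision", so DNACPR prevalence is 0.70 × 0.20 = 0.14, or 420 of the planned 3000. The plan's only numerical target for WP3 is harm: 3000 × 0.065 = 195, stated as 200, which reproduces. It gives no figure for stay.

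**Assumptions not in the protocol.** Mean stay μ = 8 days. A share f of the decisions on file at census was made at admission, and the rest arise at a constant rate. Decisions have no effect on discharge. Status is that on the assessment day, which is inferred from the synchronised data collection and not stated.

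**Closed form, exponential stays.** At census, elapsed and remaining stay are independent, each with mean μ, so mean total stay is 2μ = 16 days against 8 per admission. Let P = 0.14, p = f × P, and c = (P − p)/(1 − p), the chance that a patient without a decision at admission has one by census. Then:

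- mean elapsed stay without a decision = μ(1 − c)
- mean elapsed stay with a decision = μ[1 − (1 − P)(1 − c)]/P
- false gap = μc/P, since remaining stay is μ in both groups

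| Made at admission (f) | c | Total stay, DNACPR v not (days) | False gap (days) |
|---|---|---|---|
| 100% | 0 | 16.00 v 16.00 | 0 |
| 80% | 0.028/0.888 = 0.0315 | 17.55 v 15.75 | 1.80 |
| 50% | 0.07/0.93 = 0.0753 | 19.70 v 15.40 | 4.30 |
| 0% | 0.14 | 22.88 v 14.88 | 8.00 |

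The gap scales with μ: at a mean of 5 days and f = 0 it is 5 days. For any ReSPECT decision (P = 0.70, μ = 8), f = 50% gives c = 0.35/0.65 = 0.538 and a gap of 8 × 0.538/0.70 = 6.2 days.

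**Other stay distributions (simulated, mean 8, DNACPR 14%).** Gamma with shape 2 gives 15.5 v 11.4 (f = 0), 13.9 v 11.7 (50%) and 12.8 v 11.9 (80%), about half the exponential gaps. Lognormal with log-SD 1 gives about 35.9 v 19.5 (50%) and 28.3 v 20.7 (80%). All gaps vanish at f = 100%.

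**Would it stand out?** With exponential stays the census variance of total stay is 2μ² = 128. The standard error for 420 v 2580 patients is about √(128/420 + 128/2580) = 0.6 day, so a false gap of 4 days would look clear.

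**Testing the remedy.** Stay counted from the assessment day shows no gap with exponential stays. With lognormal stays and f = 50% it is still 14.3 v 10.3 days. Stratifying remaining stay by elapsed stay cuts the difference to about 0.2 day.

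**Testing the weight.** Weighting by 1/total stay recovers the per-admission mean of 8 days. Applied to census-day status it estimates the average fraction of a stay with a decision on file. For exponential stays and f = 50%, with r = c/(1 − c) = 0.0814, that is 0.07 + 0.93 × [1 − ln(1 + r)/r] = 0.106. The proportion of admissions ever having a decision is 0.07 + 0.93 × 0.0753 = 0.14.

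**The case against.** The strongest reply is that section 2.1 places about 70% of in-patients' forms at admission, the same 70% that section 5.5 expects in total. On that reading essentially all decisions are made at admission and the gap is nil. This stands as far as it goes: the protocol gives no share of later decisions, so the size cannot be fixed. It does not dispose of the point, because the same section names in-stay prompts and section 3.2.4 plans for forms completed later.

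A reader might infer that the census alone makes DNACPR patients appear to stay longer, by construction. The documents do not support that. Length-biased sampling lengthens both groups alike; only status gained during the stay separates them.

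A reader might also infer that the study will conclude that plans prolong admission. Nothing says so. Stay is absent from section 5.3.1 and from every regression in section 5.5. It enters only through a descriptive summary in exploratory work, and the stated decision rule concerns harm.

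Nor is over-representing long stays wrong for the aim in section 5.1.1, which is how widely ReSPECT is used among patients in hospital. That is a point-prevalence question, and a census answers it.

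Finally, a time origin can be an analysis-plan detail. But the sampling, the outcome and the grouping are all set in the protocol, and together they give the comparison described here.

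**Conclusion.** The point holds in a limited form. To the extent that decisions are made after admission, whole-admission stay by status is not a fair comparison, and the bias runs towards longer stays in the decision group. Under the stated assumptions (mean 8 days, 14% DNACPR, exponential stays) the false gap runs from 0 to 8 days. It is about half that for gamma stays with shape 2 and larger for lognormal stays. Mean stay, distribution and timing are all assumed. If status were taken as any decision during the admission instead of status on the day, the distortion would be larger: with exponential stays and half of decisions at admission, the DNACPR ratio of mean stays rises from 1.28 to 1.40. Severity is minor, because stay is descriptive and WP3's main conclusion rests on harm.

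**What to change.** In sections 5.3 and 5.5:

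- Define stay for comparisons as days from the assessment day to discharge or death, by status on the assessment day.
- Always stratify by, or adjust for, days already in hospital on that day. Counting from the assessment day alone is not enough if stays are right-skewed.
- State that whole-admission stay by status is not to be interpreted as a comparison.
- If a per-admission mean stay or survival is reported, weight each patient by 1/total stay. Do not use that weight for per-admission ReSPECT or DNACPR use; report use as point prevalence among in-patients.

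The cost is a small amount of extra analysis, plus confirmation that admission and assessment dates are on the CRF. Section 5.3 names neither date, although length of stay cannot be derived without the admission date.

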5.3.1 Outcomes

As our measure of patient harm we will use the data collected for the NHS Safety Thermometer. In participating Acute Trusts this point of care survey collects data on 100% of inpatients for one day each month. Our outcome of interest in the Classic Thermometer is 'harm free care' defined as none of the defined adverse events being present on the day of the assessment (pressure ulcers, urine infections in catheterised patients, falls, or venous thromboembolism). These are all events that would be associated with less intense care. If as a consequence of a DNACPR order, there are more of these events we will conclude that more work is needed to prevent iatrogenic harms caused by DNACPR orders leading to a lower level of care.

A second harm measure, the 'Medication Thermometer', is being rolled out in the NHS. This also a point of care survey collecting data on 100% of in-patients for one day each month. Our outcome of interest here is 'drug induced harm'. The survey identifies people who are using a specified list of high-risk medicines. There is then a discussion between a nurse, doctor and a pharmacist to assess if the patient has been harmed and the level of any harm. Harm will be defined as a moderate (or greater) incident which results in a moderate increase in treatment and which caused significant but not permanent harm. We will collect Medication Thermometer data where it is routinely available.

Standardisation of Data collection: NHS Safety Thermometer data will be extracted by NHS audit, clinical or site research staff who have been trained in the use of the tool. We are aware of variation in Thermometer measurements and will develop a training set of standardised cases in to improve consistency. We will work closely with the six sites to ensure the approach is standardised and report on reliability from the standardised cases.

